**The main indicator of the treatment efficiency:**

Changes in mean values of the bone resorption marker (collagen type 1 C-telopeptide) at the end of the study (V4) from the baseline (V1) in comparison between the groups.

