**PROJECT SYNOPSIS**

Study Title	Comparative effects of moxonidine and bisoprolol on bone metabolism, vascular and cellular markers of aging, blood pressure in hypertensive postmenopausal women
Study Sponsor:	Autonomous Nonprofit Organization "Society of experts in innovative technologies in medicine" (ANO "OSO ITEM")
Principal Investigator	[name], MD, PhD, professor
Therapeutic area / indication	Cardiology, essential hypertension
Study objectives and goals	
Primary Objective:
 
To investigate the effect of moxonidine versus bisoprolol on collagen type 1 C-telopeptide in postmenopausal female patients with arterial hypertension and osteopenia.
 
Secondary Objectives:
 
 
1. To investigate the effect of moxonidine versus bisoprolol on bone metabolism and bone tissue density in postmenopausal female patients with essential hypertension and osteopenia.
 
2. To investigate the effect of moxonidine versus bisoprolol on the processes of cellular and vascular aging in postmenopausal female patients with essential hypertension and osteopenia.
 
3. To investigate efficacy of antihypertensive therapy with moxonidine versus bisoprolol in hypertensive postmenopausal women.
 

Study Design	
Randomized, open-label, interventional, comparative clinical trial
 
Study population is postmenopausal women with essential hypertension and osteopenia. The study will enroll 114 patients after screening (it is expected that 300 patients will need to be screened to reach this enrolment goal).
 
After the informed consent signing, the patient's participation in the study will include the period before the studied product administration, treatment period and a final visit.
 
Patients will be randomized to one of two groups: moxonidine group or bisoprolol group.
 
According to the study protocol, patients randomization to the control and investigated groups will be carried out using a simple envelopes method and, therefore, it is assumed that the control and the main groups will be matched by the basic measured parameters; the number of subjects in the main and control groups is planned to be equal.
 
The study endpoints are measured prior to the studied product initiation (V1) and after completion of 48-week treatment with the investigated product (V4).

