## **3. PROGRAM PLAN AND PROCEDURES**

### **3.1 General design**

This is explorative, randomized, open-label, interventional, comparative clinical trial.

Study population is postmenopausal women with essential hypertension and osteopenia. The study will enroll 114 patients after screening (it is expected that 300 patients will need to be screened in order to reach this enrollment goal).

After the informed consent signing, the patient's participation in the study will include the period before the studied product administration, the treatment period and the final visit.

Patients will be randomized to one of two groups: moxonidine group or bisoprolol group.

According to the study protocol, patients randomization to the control and investigated groups will be carried out using a simple envelopes method and, therefore, it is assumed that the control and the investigated groups will be matched by the basic measured parameters; the number of subjects in the main and control groups is planned to be equal.

The study endpoints are measured prior to the studied product initiation (V1) and after completion of 48-week treatment with the investigated product (V4).

The period prior to the studied treatment initiation is designed to assess the patient meeting inclusion criteria and to carry out 7-10-day washout period in patients with previous antihypertensive therapy. The planned duration of the period before the treatment initiation does not exceed 14 days after the signing of the informed consent form by the patient.

Then, at the enrollment visit during the treatment period, the investigator will assess the patient meeting the inclusion criteria. If the inclusion criteria are met, the patient will be enrolled in the study. The baseline condition data will be obtained from the patient, and then the patient will be randomized to one of the two treatment groups (moxonidine or bisoprolol). The treatment period involves the enrollment visit (V1), and 3 more visits.

The final visit 4 is carried out at week 48 after the enrollment visit, the patient then completes the study.

The patients' treatment includes gradual titration of the studied products doses.

Group 1 will receive moxonidine with the dose titrated to a maximum, and then, if necessary, the patient will be shifted to the combination therapy (Step 2 – adding an ACE inhibitor)

[figure not shown]

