### 3.2 Patients randomization and identification

The study participants are randomized using a simple envelopes method. An independent person will generate a random table for 114 records in which 57 will be marked as “M” and 57 will be marked as “B”. According this computer based randomization table cards with letter “B” or “M” will be sealed in 114 numbered envelopes. The randomization table will also be sealed in a separated envelope. The numbered envelopes will be sent to Principal Investigator. The envelope with randomization table will be stored in the Sponsor file.

Each patient is assigned with a special identification code that is only used in the program. The code is assigned to a patient after enrollment and includes the health care facility code and the patient number.

According to the protocol, decoding keys for the identification codes are not provided. Persons authorized by the Sponsor, health care or other regulatory authorities may inspect any program data available to the investigator.

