### **3.6.2 Enrollment visit (V1)**

Enrollment visit is conducted no later than 14 days after signing the informed consent form by the patient.

The investigator documents all significant changes in the history of hypertension and concomitant treatment (including fast acting antihypertensives to relieve a hypertension episode that may be administered during the washout period); the investigator identifies and documents adverse events associated with the protocol procedures, if any, starting from the date of the informed consent signing.

The investigator conducts a physical examination of the patient by organs and organ systems that must include measurement of heart rate, systolic and diastolic blood pressure according to ESH/ESC recommendations that are listed in Appendix 1 [17]. Blood pressure and heart rate are measured in a sitting position after 5 minutes of rest on the arm with the highest BP during screening. Three measurements are done; the average value of the measurements is documented. The investigator assesses hypertension severity and grade according to the ESH/ESC recommendations that are listed in Appendix 2.

Applanation tonometry method is used to measure changes in patient's PWV; duplex ultrasonography of extracranial brachiocephalic arteries is employed to evaluate IMT and subclinical atherosclerosis.

Blood is sampled to investigate bone metabolism: osteocalcin, Ctx, OPG, RANKL.

Blood is sampled to determine telomerase activity.

The investigator may enroll the patient in the study and start the investigated treatment only if the patient meets all the screening criteria to start the treatment.

The investigator randomizes patients to one of two treatment groups by means of the simple envelopes method.

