## **10 STATISTICS**

### **Statistical Analysis**

#### **10.1 General methods of analysis**

Statistical analysis will be conducted under the supervision of a responsible biostatistician. The details of statistical analysis will be provided in the statistical analysis plan in accordance with the GCP requirements and other relevant requirements and laws. The statistical analysis plan will be finalized before the data lock point. All deviations from the final statistical plan version will be justified in the final program report.

The results will be combined for the complete study sample. Two-sided levels of significance and confidence intervals will be calculated. The significance of differences will be calculated for two-sided tests, with a critical significance level of 0.05.

For parameters of interval scale type, the following will be calculated: the arithmetic mean (95% confidence interval for the mean), standard deviation, median, 25th and 75th percentiles. For parameters of ordinal scale type, median, 25th and 75th percentiles will be calculated. For parameters of nominal scale type, frequency categories and confidence intervals for the frequencies (modified Wald method) will be calculated. If the assumptions made during the preliminary study planning are found to be erroneous, the analysis methods will be modified to conduct a more suitable analysis. The result of the primary endpoint analysis will be presented as an absolute number and proportion (%) of patients with target BP (<140/90 mm Hg) achieved at visit V4.

Statistical analysis will be carried out using SPSS/PASW Statistics software package (version 18), SPSS Inc., Chicago, Illinois, USA.

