#### **10.5 Sample size rationale**

As this is an explorative study with open design no formal sample size calculation was performed. The focus of the study is to obtain scientific data for a publication and taking into account a reason of feasibility of enrollment to timelines and screening of 300 patients per year in assumption that ratio of screened / enrolled patients is approximately 3 to 1 so it is expected that not less than 100 patients but no more than 114 patients will be enrolled in the study. According to this approach the total sample size is chosen 114 subjects.

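### The primary CTX contrast is stated as a difference in change, with no baseline covariate and groups assumed matched; prespecifying adjustment for V1 CTX would recover precision at almost no cost

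*Combined protocol and SAP*

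**What the plan says.** The primary endpoint has the same content in the synopsis, 3.10, 6.1 and 10.3: "Changes in mean values of the bone resorption marker (collagen type 1 C-telopeptide) at the end of the study (V4) from the baseline (V1"), compared between the groups. None of these places names a test, a model or a covariate.

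On baseline comparability, 3.1 says that because patients are randomised by envelope "it is assumed that the control and the investigated groups will be matched by the basic measured parameters". The synopsis and 3.5 say the same. Section 3.2 describes the list: "An independent person will generate a random table for 114 records in which 57 will be marked as" moxonidine and 57 as bisoprolol, with no stratification factor.

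Baseline CTX is available. Section 3.6.2 (V1, before the first dose) states "Blood is sampled to investigate bone metabolism: osteocalcin, Ctx, OPG, RANKL", and the schedule in 3.4 repeats CTX at V3 and V4.

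Section 10.1 plans "two-sided tests, with a critical significance level of 0.05" and leaves further detail to a statistical analysis plan; the documents contain no text that supplies a covariate. It also says, as does the synopsis, that the primary endpoint result will be shown as the number and percentage of patients at target BP at V4, which does not fit a CTX endpoint. Section 10.3 places efficacy in the per-protocol set and says that results will be presented descriptively.

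**The concern.** V1 CTX enters the stated contrast only by subtraction. Subtraction is full adjustment only if V4 tracks V1 one for one. Otherwise part of any baseline gap stays in the difference in change, with the opposite sign, because the arm that starts higher tends to fall more. A fixed 57/57 list balances numbers, not CTX, so assuming matched groups does not remove this.

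What is at stake is precision in the one comparison the trial is built around. Section 10.5 says "no formal sample size calculation was performed", so there is no documented reserve of power to absorb the loss. The form of contrast is the same for osteocalcin, RANKL, BMD, telomerase, PWV and IMT.

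**Working it through.** **The plan's own figure.** Section 10.5 rests on feasibility: 300 screened at about 3 to 1 gives 300/3 = 100. This reproduces the floor in "not less than 100 patients but no more than 114 patients will be enrolled" but not 114, which is the cap (300/114 = 2.63 to 1). The documents give no effect size, SD or power, so no power-based figure can be reproduced.

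**Inputs.** From the documents: 57 per arm (3.2); two-sided 0.05 (10.1). Assumed: V1–V4 correlation ρ from 0.3 to 0.9; equal SDs at the two visits; a common slope in both arms. Results are in units of the CTX SD.

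**Variances**, with n per arm:
- difference in mean change: (2/n) × 2(1−ρ)
- ANCOVA-adjusted difference: (2/n) × (1−ρ²)
- ratio: (1−ρ²) / [2(1−ρ)] = (1+ρ)/2

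At ρ = 0.5, 2/57 = 0.0351. The change-score variance is 0.0351 × 1.00 (SE 0.187) and the ANCOVA variance is 0.0351 × 0.75 (SE 0.162). The detectable difference at 80% power is (1.960 + 0.842) × SE.

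| ρ (assumed) | SE, change | SE, ANCOVA | Variance reduction | Detectable difference, change → ANCOVA | Power of change score where ANCOVA has 80% |
|---|---|---|---|---|---|
| 0.3 | 0.222 | 0.179 | 35% | 0.621 → 0.501 | 61.7% |
| 0.5 | 0.187 | 0.162 | 25% | 0.525 → 0.454 | 67.9% |
| 0.7 | 0.145 | 0.134 | 15% | 0.406 → 0.375 | 73.3% |
| 0.9 | 0.084 | 0.082 | 5% | 0.235 → 0.229 | 78.0% |

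**Baseline gap.** Its SE is sqrt(2/57) = 0.187 SD, with a 95% range of ±1.96 × 0.187 = ±0.37 SD. The chance of a gap above 0.2 SD is 29%, and above 0.3 SD it is 11%. With 50 evaluable per arm (an assumption; the documents give no dropout rate), the SE is 0.200 SD, the range ±0.39 SD, and the chance of a gap above 0.2 SD is 32%.

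**Shift in a single allocation.** The change contrast moves by −(1−ρ) × gap. At the 95% limit of 0.37 SD, the size of the shift is 0.26, 0.18, 0.11 and 0.04 SD at ρ = 0.3, 0.5, 0.7 and 0.9. At the median gap, about 0.67 × 0.187 = 0.13 SD, it is about 0.06 SD at ρ = 0.5 and 0.04 SD at ρ = 0.7, or roughly 0.34 and 0.26 of the SE.

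**These are one loss, not two.** In units of 2/n, 2(1−ρ) − (1−ρ²) = (1−ρ)², which is exactly the variance of the shift. At ρ = 0.5: 1.00 = 0.75 + 0.25.

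**Simulation check** (10,000 trials, 57 per arm). The variance ratio was 0.758 at ρ = 0.5 (formula 0.75) and 0.854 at ρ = 0.7 (formula 0.85). The slope of the change contrast on the gap was −0.50 and −0.30; for ANCOVA it was about 0. Both estimators averaged close to the true value of zero.

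**The case against.** **The text does not say raw.** A reader might infer that the plan commits to an unadjusted change score. It does not: it defines an endpoint and is silent on the model. A change endpoint is compatible with ANCOVA, since regressing change or V4 on arm and V1 gives the same treatment estimate. This stands, so the point is conditional on the contrast being analysed as written. The model still has to be stated, and the text on matching suggests that no adjustment was in view.

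**Randomisation already protects the comparison.** A reader might infer that chance imbalance biases the result on top of the precision loss. It does not. Over repeated randomisations the difference in change is unbiased in the full randomised set, and its confidence interval already contains the imbalance component. In the planned per-protocol set, however, imbalance need not be due to chance alone. Adjusting for V1 CTX does not cure that selection; it removes only what baseline CTX carries.

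**The gain may be small.** It depends on ρ, which the documents do not give for CTX or any secondary endpoint. At 0.9 the benefit is slight.

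**The study is exploratory.** True, and no stated power claim fails. But two-sided testing at 0.05 and publication are planned, so the precision of the primary contrast still matters.

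**Conclusion.** The point holds as a matter of efficiency and specification. The plan states the primary contrast as a difference in change, names no baseline covariate and relies on assumed matching, while collecting the value that would sharpen the estimate. If nothing is adjusted, the variance forgone is 35% at ρ = 0.3, 25% at 0.5, 15% at 0.7 and 5% at 0.9. This assumes equal SDs at V1 and V4 and a common slope, and ρ is an assumption throughout. The SE of the baseline gap is 0.187 SD at 57 per arm and larger among completers.

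A reader might also infer that every endpoint must be analysed as a ratio on the log scale. The documents do not support that. They give no CTX distribution, a log analysis replaces a difference in mean change with a ratio, and BMD expressed as a T-score is negative in this population (the inclusion range is −1 to −2.5) and cannot be logged.

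**What to change.** - **Primary model.** In the synopsis, 6.1 and 10.3, prespecify ANCOVA of V4 CTX (or its change) on arm and V1 CTX, and report the adjusted between-group difference with its 95% CI.
- **Scale.** Choose the log or untransformed scale before database lock. If log, say that the result is a ratio and enter V1 CTX on the same scale.
- **Secondary endpoints.** Use the same model, each with its own baseline, for osteocalcin, RANKL, BMD, telomerase, PWV and IMT, on a scale suited to each. Do not log BMD if it is a T-score. The schedule in 3.4 places the only pre-treatment BMD scan at screening, so name that value as its baseline.
- **Matching.** Remove the assumption of matched groups from the synopsis, 3.1 and 3.5.
- **Conflict on the primary result.** Reconcile the sentence in 10.1 and the synopsis that presents the primary result as a target-BP proportion with the CTX endpoint in 3.10, 6.1 and 10.3.

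The cost is wording and one degree of freedom per model; no new data are needed.

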**Secondary efficiency indicators:**

- Changes in mean values of telomerase at the end of the study (V4) from the baseline (V1).
- Changes in mean values of Hs-CRP, lipids, PWV and IMT at the end of the study (V4) from the baseline (V1).
- Changes in mean values of the bone synthesis and resorption markers (osteocalcin, collagen type 1 C-telopeptide) at the end of the study (V4) from the baseline (V1).
- Changes in mean values of the bone synthesis marker (osteocalcin) at the end of the study (V4) from the baseline (V1).
- Changes in mean values of the receptor activator of nuclear factor kappa-B ligand (RANKL) at the end of the study (V4) from the baseline (V1).
- Changes in mean values of BMD at the end of the study (V4) from the baseline (V1).

- Proportion of the treatment responders (defined as the proportion (%) of patients who achieved target blood pressure <140/90 mmHg) after 8, 24 and 48 weeks of the investigated treatment (V2, V3 and V4).

The treatment efficacy will be evaluated on visits V2, V3 and V4 based on SBP and DBP measurements. Clinical response to the treatment is defined as follows:

- Responders: hypertension control, if BP <140/90 mmHg at the visit.
- Non-responders: uncontrolled hypertension, if BP  $\geq$ 140/90 mmHg at the visit.

The efficacy results will be presented using descriptive statistics. Historical control (publications data) will be used to interpret the results.

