## **2. PROGRAM OBJECTIVES**

**2.1 Primary objective:** To investigate the effect of moxonidine versus bisoprolol on collagen type 1 C-telopeptide in postmenopausal female patients with arterial hypertension and osteopenia.

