### **2.2 Secondary (experimental) objectives:**

To investigate the effect of moxonidine versus bisoprolol on bone metabolism and bone tissue density in postmenopausal female patients with essential hypertension and osteopenia.

To investigate the effect of moxonidine versus bisoprolol on the processes of cellular and vascular aging in postmenopausal female patients with essential hypertension and osteopenia.

To investigate efficacy of antihypertensive therapy with moxonidine versus bisoprolol in hypertensive postmenopausal women.

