## **4 PATIENT SCREENING AND EXCLUSION**

### **4.1 Patient Population**

Postmenopausal women with essential hypertension and osteopenia treated with moxonidine.

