### **6.2 Secondary endpoints efficacy criteria:**

1. Changes in mean values of the bone synthesis marker (osteocalcin) at the end of the study (V4) from the baseline (V1) and to compare the values between the groups.
2. Changes in mean values of the receptor activator of nuclear factor kappa-B ligand (RANKL) at visit 4 versus baseline level (visit 1) and to compare the values between the groups

3. Changes in mean values of BMD at visit 4 versus baseline level (visit 1) using control dual-energy X-ray absorptiometry and to compare the results between the groups
4. Changes in mean values of telomerase activity at visit 4 versus baseline level (visit 1) and to compare the values between the groups
5. Changes in mean values of pulse wave velocity (PWV) at visit 4 versus baseline level (visit 1) and to compare the values between the groups
6. Changes in mean values of intima-media thickness (IMT) at visit 4 versus baseline level (visit 1) and to compare the values between the groups
7. Proportion of the treatment responders (defined as the proportion (%) of patients who achieved target blood pressure <140/90 mmHg) after 8 and 48 weeks of the investigated treatment (V2, V3 and V4) and to compare the values between the groups.

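### Section 10.3 reads efficacy against an unspecified historical control and omits the between-group comparison from every secondary indicator, contradicting the objectives, section 6.2 and its own primary indicator

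*Combined protocol and SAP*

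**What the plan says.** Section 3.2 provides 114 envelopes, 57 for each drug. The primary objective (2.1) is "To investigate the effect of moxonidine versus bisoprolol on collagen type 1 C-telopeptide". The three secondary objectives (2.2) use the same contrast, for example "To investigate efficacy of antihypertensive therapy with moxonidine versus bisoprolol in hypertensive postmenopausal women".

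The analysis text does not follow this consistently:

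- **Section 10.3, main indicator:** CTX change at V4 is taken "from the baseline (V1) in comparison between the groups".
- **Section 6.2:** secondary criteria carry "and to compare the values between the groups" or an equivalent phrase.
- **Section 10.1 and synopsis:** "The significance of differences will be calculated for two-sided tests, with a critical significance level of 0.05".
- **Section 10.3, secondary indicators:** each bullet gives only a change from V1 to V4, or a proportion of responders. None mentions the other arm. The list ends with "The efficacy results will be presented using descriptive statistics. Historical control (publications data) will be used to interpret the results".

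Three other sentences bear on the same point. Section 10.1 and the synopsis say "The results will be combined for the complete study sample". Both also say that the primary endpoint result will be shown as the number and percentage of patients at target blood pressure at V4, although the primary endpoint is CTX. Section 4.1 gives the population as "Postmenopausal women with essential hypertension and osteopenia treated with moxonidine".

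**The concern.** A randomised trial with a concurrent active comparator has no need of a historical control to interpret efficacy. Yet that sentence is the only one in the plan that says how efficacy results are to be interpreted. It is not restricted to the secondary indicators, and it cites no publication, value or method.

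A change within one arm over 48 weeks mixes any drug effect with other influences: withdrawal of earlier antihypertensives (5.1), lifestyle advice given at screening (3.6.1), calcium with vitamin D (3.8.5) and assays run by each site's own method (Table 2 in 3.7). Randomisation balances these between arms in expectation, so they cancel in the difference between arms. They need not cancel against a published series with another population and another assay, and what is left over would be read as drug effect.

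The trial is also open-label. An unnamed external comparator could be chosen after results are visible.

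**Working it through.** **Step 1. Is the between-group comparison stated for each endpoint?**

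| Endpoint | Synopsis, efficacy analysis | 3.10 | 6.1 / 6.2 | 10.3 |
|---|---|---|---|---|
| CTX (primary) | yes | yes | yes | yes as main indicator; no where it recurs in the secondary list |
| Osteocalcin | not listed | yes | yes | no |
| RANKL | yes | yes | yes | no |
| BMD | yes | yes | yes | no |
| Telomerase | yes | yes | yes | no |
| PWV | yes | yes | yes | no |
| IMT | yes | yes | yes | no |
| Target BP | no | no | yes | no |
| hs-CRP, lipids | not listed | not listed | not listed | no |

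The 10.3 secondary list is the outlier. Purely descriptive presentation also does not fit the two-sided tests in 10.1. Nowhere is a between-group estimate, test or model named. The confidence interval specified for continuous measures is for a mean, not for a difference.

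**Step 2. Is there a planned figure to reproduce?** Only the total of 114, which rests on feasibility (10.5). Screening 300 at about 3 to 1 gives 300/3 = 100, the stated minimum. The 114 is the stated cap and needs 300/114 = 2.63 to 1. No effect size, SD, power or dropout is given, so there is no power figure to check.

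**Step 3. What can the randomised comparison deliver?** Normal approximation, two-sided 0.05, in SD units of the outcome analysed:

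- Detectable difference = (1.960 + z for power) × √(2/n). At n = 57 and 80% power: (1.960 + 0.842) × 0.1873 = 0.52.
- 95% CI half-width = 1.960 × √(2/n). At n = 57: 1.960 × 0.1873 = 0.37.

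| n per arm | 80% power | 90% power | CI half-width |
|---|---|---|---|
| 57 (full enrolment) | 0.52 SD | 0.61 SD | 0.37 SD |
| 50 (stated minimum of 100) | 0.56 SD | 0.65 SD | 0.39 SD |
| 40 (assumed per-protocol set) | 0.63 SD | 0.72 SD | 0.44 SD |

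**Step 4. What could the historical comparison do?** The plan names no test, so this is an illustration. Suppose one arm of n = 57 is tested against a fixed published mean that lies b SD from the value these patients and assays would show with no drug effect. The rejection rate is 1 − Φ(1.960 − b√n) + Φ(−1.960 − b√n), with √57 = 7.55. For b = 0.2, b√n = 1.51, which gives 1 − Φ(0.45) + Φ(−3.47) = 32.7%.

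| Assumed b | Rejection rate with no drug effect |
|---|---|
| 0 | 5.0% |
| 0.1 | 11.7% |
| 0.2 | 32.7% |
| 0.3 | 62.0% |

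A mismatch with the literature affects both arms alike and drops out of their difference.

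**Step 5. The same point on the CTX scale, with assumed figures.** Let a shared non-drug shift of −10% occur in both arms and be absent from the published series. The historical comparison then reads −10 points as drug effect. The randomised contrast is −10 − (−10) = 0.

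**The case against.** The strongest reply is that the randomised comparison is plainly in the plan. Section 10.3 states it for CTX, as do the synopsis, 3.10 and 6.1, and 10.1 tests differences at 0.05. The synopsis and 3.10 state it for most secondary endpoints, so its absence from the 10.3 list may be loose drafting. The historical-control sentence sets no decision rule and can be read as a promise to discuss the literature. The trial is exploratory, and 10.1 defers detail to a statistical analysis plan.

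Much of this stands, and it rules out two stronger readings.

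- **A reader might infer that the randomised comparison does not drive the conclusion.** The documents do not say which comparison decides. They contradict each other, and 10.3 itself keeps the contrast for the primary endpoint.
- **A reader might infer from "The results will be combined for the complete study sample" that the two arms will be pooled.** The sentence does not say so. The protocol refers to facility codes (3.2), every study site (11) and every participating country (13.3), so pooling across sites is at least as natural a reading, and it is the one that agrees with the between-group CTX indicator.

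Section 4.1 carries little weight either. The synopsis and 3.1 describe both groups, so 4.1 is a wording slip.

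The reply does not remove the core. The exploratory label explains the lack of a formal sample size calculation, but it does not make an external comparator suitable when a randomised one is at hand. No separate analysis plan is in the text available. Such a plan need only be final before data lock, and 10.1 allows methods to be modified.

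**Conclusion.** The concern holds as an internal contradiction with an inferential consequence. Section 10.3 sets out descriptive results read against an unspecified, non-concurrent comparator and leaves the between-group comparison out of all its secondary indicators. That conflicts with the objectives, section 6.2, the primary indicator in 10.3 and the tests in 10.1. No between-group estimate or model is defined to settle the conflict.

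The error from a historical comparison cannot be sized from the documents, because no source is named. The rates of 11.7% to 62.0% rest on assumed offsets of 0.1 to 0.3 SD, a fixed published value and a formal test that the plan does not specify. The −10% example is also an assumption, including the absence of that shift from the published series. The 0.52 SD figure follows from 57 per arm if all are analysed. Section 10.3 analyses per-protocol completers, so the number will be smaller if patients are lost, and the balance given by randomisation is then less secure. That is a separate matter, and it does not favour the historical comparison.

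**What to change.** Make these changes before data lock:

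1. **10.3, closing sentences:** delete the historical-control sentence or limit published data to discussion context.
2. **10.3, basis for conclusions:** state that conclusions on CTX and the continuous secondary endpoints rest on the concurrent randomised moxonidine-minus-bisoprolol difference in V1-to-V4 change with its 95% CI, for example from an ANCOVA of the V4 value on arm and V1 value. For target BP, use the difference in proportions with its 95% CI.
3. **10.3, secondary indicators:** restore the comparison between groups, in line with 6.2.
4. **10.1 and synopsis, combined results:** make clear that the two arms are not pooled for efficacy.
5. **10.1 and synopsis, primary result:** replace the target-BP presentation with the between-arm CTX difference.
6. **4.1:** align the wording with both arms.

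The cost is wording in 10.1, 10.3, 4.1 and the synopsis. The analyses use V1 and V4 CTX and secondary-endpoint data, and blood pressure readings, that the visit schedule already collects. No extra patients, visits or samples are needed.
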